| Sample size calculation | 
The sample size has been calculated to verify equivalence between the test treatment (HFA-152a) and the reference treatment (HFA-134a) for the relative change from baseline in FEV1 at the 15 min post-dose timepoint, with equivalence defined as a difference between the two treatments within the <math>\pm 10\%</math>.
 
A total of 20 evaluable subjects will ensure a 95% power to provide a 95% confidence interval (CI) of the mean difference of the relative change from baseline in FEV1 at 15 min post-dose within the above-mentioned equivalence limits (i.e. [-10%; +10%]) assuming a within-subject standard deviation (SD) of 8%.
 
Estimating a non-evaluable rate of 16%, a total of 24 subjects will be randomised.
  |
| Statistical methods     | 
Safety variables
 
Variable assessing the primary objective of the study (potential for bronchoconstriction of each propellant):
 
 
The relative change from baseline in FEV1 at the 15 min post-dose timepoint will be analysed using an analysis of covariance (ANCOVA) model, including treatment group, subject and period as fixed effects, and FEV1 baseline (mean of the two measurements at 45 min and 15 min pre-dose in each treatment period) as a covariate.
 
 
The adjusted mean relative change from baseline obtained with each treatment and the adjusted mean difference between HFA-152a and HFA-134a with their 95% CIs and p-values will be estimated by the model.
 
Variables completing the evaluation of the potential for bronchoconstriction of each propellant:
 
 
The relative changes from baseline in FEV1 at all the other post-dose timepoints (5 min and 30 min, 1 h, 1 h 30 min and 3 h after T1) will
 
 |

|  |                      |
|--|----------------------|
| Clinical Study Code No.: CLI-05993AB6-07 | Version No.: 2.0     |
| EUDRACT No.: 2022-000536-36              | Date: 30 August 2022 |

|  |  |
|--|--|

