## 3. STUDY DESIGN

This is a Phase IIa, multicentre (approximately 4 centres in the United Kingdom [UK]), single-dose, randomised, double-blind, controlled, 2-way cross-over study to evaluate the potential for bronchoconstriction of the new HFA-152a propellant (single dose, [REDACTED]) *versus* the marketed HFA-134a propellant (single dose, [REDACTED]) in adult subjects with mild asthma (Step 1 of the GINA 2021 guidelines).

A double-blind design was chosen for this study to minimise the risk of bias in the study outcomes.

The study design is shown in [Figure 1](#).

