### 6.5 Treatment Allocation

A balanced block randomisation list will be prepared using a computerised system. Each subject will be assigned to one of the two possible treatment sequences arranged in a 2x2 William design.

Each subject will be identified by a unique five-digit code (two digits specific to the investigational centre and three digits specific to each subject [XXYYY]) assigned at screening. At randomisation (TP1), each eligible subject will be assigned the lowest randomisation number available at the investigational centre according to a pre-established randomisation list:

- Subjects who do not meet inclusion and/or exclusion criteria at screening or prior to randomisation will not be eligible to enter the study. They will be considered as “screen failure subjects”;
- Subjects who fully meet inclusion and/or exclusion criteria at screening or before randomisation will be eligible to enter the study;
- Subjects who prematurely terminate the study will be considered as “drop-out subjects”. These subjects cannot be screened again.

*Note: If a subject is withdrawn or discontinued from the study after randomisation, the subject code and randomisation number will not be reassigned to another subject.*

|  |                      |
|--|----------------------|
| Clinical Study Code No.: CLI-05993AB6-07 | Version No.: 2.0     |
| EUDRACT No.: 2022-000536-36              | Date: 30 August 2022 |

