## 12. STATISTICAL METHODS

### 12.1 Sample Size

The sample size has been calculated to verify equivalence between the test treatment (HFA-152a) and the reference treatment (HFA-134a) for the relative change from baseline in FEV1 at the 15 min post-dose timepoint, with equivalence defined as a difference between the two treatments within the 10% (i.e. [-10%; +10%]).

A total of 20 evaluable subjects will ensure a 95% power to provide a 95% confidence interval (CI) of the mean difference of the relative change from baseline in FEV1 at 15 min post-dose within the above-mentioned equivalence limits (i.e. [-10%; +10%]) assuming a within-subject standard deviation (SD) of 8%.

Estimating a non-evaluable rate of 16%, a total of 24 subjects will be randomised.

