### 12.3.6 Safety Variables

Safety analyses will be based on the Safety population. For sensitivity purposes, the safety variables assessing the primary objective of the study will also be analysed in the PP population (see [Section 12.2](#)).

The safety variables of the study are presented in [Section 9](#).

The safety variable assessing the **primary objective** of the study (i.e. evaluation of the potential for bronchoconstriction of each propellant) will be analysed as follow:

- The relative change from baseline in FEV1 at the 15 min post-dose timepoint will be analysed using an analysis of covariance (ANCOVA) model, including treatment group, subject and period as fixed effects, and FEV1 baseline (mean of the two measurements at 45 min and 15 min pre-dose in each treatment period) as a covariate. The adjusted mean relative change from baseline obtained with each treatment and the adjusted mean difference between HFA-152a and HFA-134a with their 95% CIs and p-values will be estimated by the model.

The other safety variables completing the evaluation of the potential for bronchoconstriction of each propellant will be analysed as follows:

- The relative changes from baseline in FEV1 at all the other post-dose timepoints (5 min, 30 min, 1 h, 1 h 30 min and 3 h after T1) will be analysed using the same model used for the relative change from baseline in FEV1 at 15 min post-dose;
- The absolute changes from baseline in FEV1 at all post-dose timepoints (5 min, 15 min, 30 min, 1 h, 1 h 30 min and 3 h after T1) will be analysed using the same model used for the relative change from baseline in FEV1 at 15 min post-dose;
- The number and percentage of subjects with a relative change from baseline in FEV1 at each post-dose timepoint (5 min, 15 min, 30 min, 1 h, 1 h 30 min and 3 h after T1) and at any post-dose timepoint <-15% will be summarised for each treatment;
- The change from baseline in FEV1 AUC0-3h will be summarised using descriptive statistics;
- The relative and absolute changes from baseline in PEF at all post-dose timepoints (5 min, 15 min, 30 min, 1 h, 1 h 30 min and 3 h after T1) will be summarised for each treatment, using descriptive statistics;
- The number and percentage of subjects with use of rescue medication in the 3 h post-dose will be summarised for each treatment;

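### The 95% power claimed for 20 evaluable subjects comes from a normal approximation; the planned t-based analysis gives about 92%, and only if the true difference is zero

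*Protocol*

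**What the plan says.** Protocol 12.1 defines equivalence as a treatment difference within ±10% for the relative change from baseline in FEV1 at 15 minutes post-dose. It assumes a within-subject SD of 8% and states: "A total of 20 evaluable subjects will ensure a 95% power to provide a 95% confidence interval (CI) of the mean difference" lies within those limits. It then adds: "Estimating a non-evaluable rate of 16%, a total of 24 subjects will be randomised". The Protocol Outline and SAP 1.3 repeat the power statement with the same inputs. None of the three places names a formula or software, and none gives the true difference assumed.

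On design, Protocol 6.5 says: "Each subject will be assigned to one of the two possible treatment sequences arranged in a 2x2 William design". On analysis, Protocol 12.3.6 specifies an ANCOVA "including treatment group, subject and period as fixed effects", with the baseline FEV1 of each period as a covariate. SAP 2.5.3 repeats this model. The example code in SAP 9.1 fits it with PROC MIXED and takes the treatment difference from LSMEANS at alpha 0.05.

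**The concern.** Power for equivalence should describe the interval that will actually be computed. With 20 subjects in a two-period cross-over, the residual variance is estimated on fewer than 20 degrees of freedom, so the interval is wider than a normal one and its width varies from trial to trial. A formula that treats the SD as known ignores both effects and overstates the power.

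The power of an equivalence test also depends on the true difference. Zero is the most favourable value, and the plan does not say that it was used.

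The sample-size paragraph is where the plan defines equivalence and justifies the size of the trial. Protocol 1.2 explains that the study was conceived in response to a regulator's concern about a residual risk. A reader who repeats the calculation with exact cross-over methods will not obtain the stated figure.

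**Working it through.** **Inputs**

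- Evaluable subjects n = 20, within-subject SD 8, limits ±10, two-sided 95% CI: Protocol 12.1.
- Two sequences, two periods: Protocol 3 and 6.5. I assume 10 evaluable subjects per sequence.
- Model with treatment, subject, period and baseline: Protocol 12.3.6, SAP 2.5.3 and 9.1.
- True difference 0: my assumption, because the documents give none.

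**Standard error of the treatment difference**

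SE = 8 × √(2/20) = 2.530.

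**Reproducing the stated figure (normal approximation)**

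Power = 2Φ(10/SE − 1.960) − 1 = 2Φ(3.953 − 1.960) − 1 = 2Φ(1.993) − 1 = 95.4%.

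The same formula with n = 19 gives 94.2%. Solved for n, it gives 2 × 8² × (1.96 + 1.96)² / 10² = 19.7, hence 20. So 20 is the first number at which a normal formula passes 95%, which makes that formula the likely source.

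**Degrees of freedom of the planned analysis**

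Twenty complete subjects give 40 observations. Removing 1 for the mean, 19 for subjects, 1 for treatment and 1 for period leaves 18. The baseline covariate takes one more, leaving 17. The critical value is then 2.10 (18 df) or 2.11 (17 df) instead of 1.96.

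**Exact power**

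The criterion is met when the estimated difference plus and minus t × (estimated SE) stays inside ±10. Its probability is found by integrating over the chi-square distribution of the residual variance. The results at n = 20, SD 8 and true difference 0 are:

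| Method | Power |
|---|---|
| Normal approximation | 95.4% |
| Exact, 18 df | 92.4% |
| Exact, 17 df | 92.2% |
| Simulation, 2,000,000 draws, 18 df / 17 df | 92.4% / 92.2% |

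The non-central t formula with 18 df also gives 92.4%.

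**Dependence on the true difference (n = 20, 18 df)**

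| True difference (percentage points) | Exact power |
|---|---|
| 0 | 92.4% |
| 0.5 | 91.9% |
| 1 | 90.4% |
| 2 | 84.3% |
| 3 | 74.3% |

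**Dependence on the evaluable number (true difference 0, n − 2 df)**

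| Evaluable | Exact power |
|---|---|
| 20 | 92.4% |
| 22 | 95.2% |
| 23 | 96.2% |
| 24 | 97.0% |

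With n fixed at 20 and 18 df, 95% requires a within-subject SD of about 7.6 instead of 8.

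**Other readings of the text**

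A 90% CI would give 96.9%. A single limit tested at one-sided 0.025 would give 96.2%. Taking 8% as the SD of paired differences would give 99.9%. These values are above 95%, but none is the stated criterion, which is a 95% CI inside both limits with a within-subject SD.

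**Allowance for non-evaluable subjects**

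20 / (1 − 0.16) = 23.8, hence 24. This step is correct.

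**The case against.** The 95% is not a slip of arithmetic. A recognised large-sample formula reproduces it, and the three statements agree with one another. The fault is an undisclosed approximation that is optimistic by 95 − 92.4 = 2.6 points, or 2.8 points on 17 df. That description is fair, but the figure is still not the power of the analysis that the plan specifies.

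The sample-size text does not mention a t distribution, and SAP 9.1 says its code is only an example. This carries little weight, because an interval from a fixed-effects ANCOVA is t-based.

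The baseline covariate might reduce the residual variance as well as cost a degree of freedom. If the 8% is an unadjusted SD and baseline explained about 10% of the residual variance, the SD would be 8 × √0.9 = 7.59, and exact power on 17 df would be 95%. The documents do not say whether the 8% is before or after adjustment, and they claim no such gain. The possibility stands, but it does not support the figure as written.

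The primary analysis uses the Safety population, and 24 subjects are randomised, so more than 20 may contribute. With 22 or more the exact power passes 95%. This stands and limits the consequence, but the plan's claim is made for 20.

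Uncertainty in the SD matters more than t against z. With 20 subjects and 18 df, an SD of 7.5 gives 95.7%, while 8.5 gives 88.0% and 9 gives 82.6%. This is true, and it is a reason to show the assumptions, not to leave the figure unqualified.

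Finally, power falls away from zero in any equivalence trial, and the documents give no basis for expecting a difference of 2 or 3 points. Those rows are illustrations. The missing statement of the assumed difference remains a gap.

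**Conclusion.** The concern holds. With 20 evaluable subjects, a within-subject SD of 8%, limits of ±10% and a two-sided 95% CI, the planned analysis has 92.4% power on 18 df, or 92.2% on 17 df. The stated 95% requires a normal approximation. The chance of missing the criterion at the planned evaluable number is 100 − 92.4 = 7.6% rather than 5%, about half as much again (7.6/5 = 1.52). The result assumes a true difference of zero, balanced sequences, complete data in both periods for the 20 subjects, and no variance reduction from the covariate. Any non-zero difference lowers the power.

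The practical effect is modest. Power stays above 90% at zero difference, and the 24 randomised leave room to reach 95% if no more than two are non-evaluable. No estimate, interval, margin or analysis changes. The correction should be made because the same unsupported figure appears in three places and justifies the size of the trial.

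**What to change.** Replace the power sentence in Protocol 12.1, the Protocol Outline and SAP 1.3 with wording such as: 20 evaluable subjects give about 92% power for the t-based 95% CI of the treatment difference to lie within ±10%, assuming a true difference of 0 and a within-subject SD of 8%; if all 24 randomised subjects are evaluable, the power is about 97%. Name the calculation method, and add the power with 20 evaluable subjects at a true difference of 1 and 2 percentage points (90.4% and 84.3%).

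The cost is wording only, with a slightly less favourable headline figure. The number randomised, the margin and the analysis stay as they are. If the sponsor would rather keep 95% as a formal target, 22 evaluable subjects are needed. At the same non-evaluable rate that is 22/0.84 = 26.2, hence 27 randomised, but the correction does not require this.

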### 12.2 Populations for Analysis

- **Safety population:** all randomised subjects who receive at least one dose of any of the two study treatments (analysed as treated);
- **Per-protocol population (PP):** all subjects from the Safety population, except those subjects with important protocol deviations impacting the analysis population. Exact definition of important protocol deviations impacting the analysis population will be discussed by the study team during the blind review of the data and described in the Data Review Report.

Since a cross-over design will be used, the inclusion in the populations for analysis will be defined on a per-period basis.

The Safety population will be used for the analysis of all safety variables. The variables assessing the primary study objective will also be analysed considering the PP population, for sensitivity purposes.

### 12.3 Statistical Analysis

A detailed statistical analysis plan will be described in the Statistical Analysis Plan (SAP), which will be finalised before breaking the blind.

#### 12.3.1 Descriptive Statistics

General descriptive statistics for numeric variables will be summarised using n (number of observed values), the mean, the 95% CI of the mean, the SD, the median and the minimum and

|  |                      |
|--|----------------------|
| Clinical Study Code No.: CLI-05993AB6-07 | Version No.: 2.0     |
| EUDRACT No.: 2022-000536-36              | Date: 30 August 2022 |

maximum values. Categorical variables will be summarised using the number and percent of subjects with a specific level of the variable.

### 12.3.2 Missing Data

As a general rule, missing data will not be imputed.

For serial spirometry-derived parameters, the following rules will apply:

- Pre-dose FEV1 and PEF:
  - In case only one pre-dose measurement is available, it will be used as pre-dose FEV1 and PEF;
  - In case no pre-dose measurements are available, the pre-dose FEV1 and PEF will be considered missing.
- FEV1 AUC0-3h calculation:
  - In case only one pre-dose measurement is available, it will be used as pre-dose value (corresponding to time 0 for the calculation of the area under the concentration-time curve [AUC]);
  - In case no pre-dose measurements are available, the entire curve will be considered missing;
  - Single, isolated missing values (different from pre-dose) will be replaced by linear interpolation using adjacent values;
  - In case of two or more consecutive missing timepoints, the entire curve will be considered missing;
  - In case of three or more missing timepoints, the entire curve will be considered missing.

Further details on dealing with missing data, along with the handling of possible outliers, will be described in the SAP. Other critical missing data, if any, will be discussed during the review of the data. Decisions will be fully documented in the Data Review Report.

### 12.3.3 Subject Demographics and Baseline Characteristics

Demographics and baseline variables will be summarised by sequence and overall, using descriptive statistics for the Safety population.

The following variables will be presented: age, gender, race, height, weight, asthma history, medical history, prior medications, physical examination, vital signs, 12-lead ECG, ACQ-5, lung function, urinalysis, and safety blood assessments (routine haematology and clinical chemistry parameters).

The following demographic and baseline variables will also be presented for the PP population: demographics (age, gender, race), asthma history and lung function.

### 12.3.4 Primary Efficacy Variables

No primary efficacy variables are considered in this study.

### 12.3.5 Secondary Efficacy Variables

No secondary efficacy variables are considered in this study.

|  |                      |
|--|----------------------|
| Clinical Study Code No.: CLI-05993AB6-07 | Version No.: 2.0     |
| EUDRACT No.: 2022-000536-36              | Date: 30 August 2022 |

### 12.3.6 Safety Variables

Safety analyses will be based on the Safety population. For sensitivity purposes, the safety variables assessing the primary objective of the study will also be analysed in the PP population (see [Section 12.2](#)).

The safety variables of the study are presented in [Section 9](#).

The safety variable assessing the **primary objective** of the study (i.e. evaluation of the potential for bronchoconstriction of each propellant) will be analysed as follow:

- The relative change from baseline in FEV1 at the 15 min post-dose timepoint will be analysed using an analysis of covariance (ANCOVA) model, including treatment group, subject and period as fixed effects, and FEV1 baseline (mean of the two measurements at 45 min and 15 min pre-dose in each treatment period) as a covariate. The adjusted mean relative change from baseline obtained with each treatment and the adjusted mean difference between HFA-152a and HFA-134a with their 95% CIs and p-values will be estimated by the model.

The other safety variables completing the evaluation of the potential for bronchoconstriction of each propellant will be analysed as follows:

- The relative changes from baseline in FEV1 at all the other post-dose timepoints (5 min, 30 min, 1 h, 1 h 30 min and 3 h after T1) will be analysed using the same model used for the relative change from baseline in FEV1 at 15 min post-dose;
- The absolute changes from baseline in FEV1 at all post-dose timepoints (5 min, 15 min, 30 min, 1 h, 1 h 30 min and 3 h after T1) will be analysed using the same model used for the relative change from baseline in FEV1 at 15 min post-dose;
- The number and percentage of subjects with a relative change from baseline in FEV1 at each post-dose timepoint (5 min, 15 min, 30 min, 1 h, 1 h 30 min and 3 h after T1) and at any post-dose timepoint <-15% will be summarised for each treatment;
- The change from baseline in FEV1 AUC0-3h will be summarised using descriptive statistics;
- The relative and absolute changes from baseline in PEF at all post-dose timepoints (5 min, 15 min, 30 min, 1 h, 1 h 30 min and 3 h after T1) will be summarised for each treatment, using descriptive statistics;
- The number and percentage of subjects with use of rescue medication in the 3 h post-dose will be summarised for each treatment;
- The mean use (puffs) of rescue medication in the 3 h post-dose will be summarised for each treatment, using descriptive statistics.

The safety variables assessing the **secondary objective** of the study (i.e. general safety and tolerability of the two different propellants) will be analysed as follow:

- **Adverse events and adverse events of particular interest:**

All AEs starting on or after the time of first study treatment intake will be classified as treatment-emergent adverse events (TEAE). Any AEs started after the informed consent signature and before the time of first study treatment intake will be classified as pre-treatment AEs.

The number of subjects who experienced at least one TEAE, ADR, serious TEAE, serious ADR, TEAE leading to study discontinuation, and TEAE leading to death will

|  |                      |
|--|----------------------|
| Clinical Study Code No.: CLI-05993AB6-07 | Version No.: 2.0     |
| EUDRACT No.: 2022-000536-36              | Date: 30 August 2022 |

be summarised for each treatment. Summaries will be presented overall (number and percentage of subjects having at least one event, total number of events) and by system organ class (SOC) and preferred term (PT) (number and percentage of subjects having at least one occurrence of that event) using the MedDRA. Specific summary tables will be provided for the AEs of particular interest (bronchospasm, cough, dysphonia, hoarseness).

All AEs will be listed.

Pre-treatment AEs will be listed only.

- **ECG**

For ECG parameters: HR, QRS, PR, and QTcF, mean absolute values and change from baseline will be summarised for each treatment using descriptive statistics. For QTcF, the following categories will also be analysed for each study treatment, by means of descriptive statistics:

- For male subjects: QTcF interval >450 ms, >480 ms and >500 ms;
- For female subjects: QTcF interval >470 ms and >500 ms;
- For both, male and female subjects: Change from baseline >30 ms and >60 ms.

The analysis will be presented at each post-dose timepoint and at any post-dose timepoint.

All data will be listed.

- **Vital signs**

Vital signs (SBP and DBP) mean absolute values at each pre-dose and post-dose timepoint and change from baseline will be summarised for each study treatment, by means of descriptive statistics.

All vital signs will be listed.

|              |
|--------------|
| • [REDACTED] |
| [REDACTED]   |
| • [REDACTED] |

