1.3 EXPECTED SAMPLE SIZE

The sample size has been calculated to verify equivalence between the test treatment (HFA-152a) and the reference treatment (HFA-134a) for the relative change from baseline in FEV₁ at the 15 min post-dose time point, with equivalence defined as a difference between the two treatments within the 10% (i.e. [-10%; +10%]).

A total of 20 evaluable subjects will ensure a 95% power to provide a 95% confidence interval (CI) of the mean difference of the relative change from baseline in FEV₁ at 15 min post-dose within the above-mentioned equivalence limits (i.e. [-10%; +10%]) assuming a within-subject standard deviation (SD) of 8%.

Estimating a non-evaluable rate of 16%, a total of 24 subjects will be randomised.

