- If the date(time) is missing or incomplete for a specific post-dose time point, then it will be imputed as the date(time) of the previous time point + the theoretical time interval between the two time points.
- If 2 or more consecutive post-dose time points have a missing or incomplete date(time), then the AUC will also be set to missing.

For FEV₁, the following abnormality categories are defined:

- Relative changes from baseline:
 - Decrease from Baseline >15 %

Potential exclusion of lung function parameters based on time window not respected will be discussed during the review of the data by the Chiesi team. Decisions on whether values are to be excluded from the analysis will be fully documented in the DRR.

2.5.3 *Inferential statistics*

Primary objective (i.e. evaluation of the potential for bronchoconstriction of each propellant):

- The relative change from baseline in FEV₁ at the 15 min post-dose time point will be analysed using an analysis of covariance (ANCOVA) model, including treatment group, subject and period as fixed effects, and FEV₁ baseline (mean of the two measurements at 45 min and 15 min pre-dose in each treatment period) as a covariate.

The adjusted mean relative change from baseline obtained with each treatment and the adjusted mean difference between HFA-152a and HFA-134a with their 95% CIs and p-values will be estimated by the model.

	Statistical Analysis Plan	
CLI-05993AB6-07		Final 1.0 of 22DEC2022

Other variables completing the evaluation of the potential for bronchoconstriction of each propellant:

- The relative changes from baseline in FEV₁ at all the other post-dose time points (5 min, 30 min, 1 h, 1 h 30 min and 3 h) will be analysed using the same model used for the relative change from baseline in FEV₁ at 15 min post-dose;
- The absolute changes from baseline in FEV₁ at all post-dose time points (5 min, 15 min, 30 min, 1 h, 1 h 30 min and 3 h) will be analysed using the same model used for the relative change from baseline in FEV₁ at 15 min post-dose.

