2.5.4 Presentation of results

Lung function parameters will be summarised by means of descriptive statistics at each analysis time point by treatment. Actual values, absolute and relative changes from baseline (FEV₁ and PEF only) will be tabulated.

For the ANCOVA models, adjusted mean in each treatment and the adjusted mean difference between HFA-152a and HFA-134a, their 95% CIs and related p-values will be provided and tabulated from the ANCOVA. This tables will also include the type III p-values associated to model effects.

The number and percentage of subjects with FEV₁ abnormal relative changes from baseline will be presented at each post-dose time point and at the worst-case analysis visit by treatment.

The change from baseline in FEV₁ AUC_{0-3h} will be summarised by means of descriptive statistics by treatment.

All lung function parameters will be listed.

Graphs of the mean changes (both absolute and relative) from baseline over time will be prepared for FEV₁ and PEF by treatment.

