	Descriptive statistics of actual values and changes from baseline in FEV ₁ and PEF results per parameter and analysis time point. Table sorted by analysis time point. Each parameter will begin on a new page.		
14.3.7.1.2	Lung Functions: Summary of Actual Values and Changes from Baseline (PP Analysis Set)	PP	TPT001
	Descriptive statistics of actual values and changes from baseline in FEV ₁ and PEF results per parameter and analysis time point. Table sorted by analysis time point. Each parameter will begin on a new page.		
14.3.7.2.1	Lung Functions: Summary of Relative Changes from Baseline (Safety Set) [KFR]	SAF	TPT004
	Descriptive statistics of relative changes from baseline in FEV ₁ and PEF results per parameter and analysis time point. Table sorted by analysis time point. Only post-baseline analysis time points are shown.		
14.3.7.2.2	Lung Functions: Summary of Relative Changes from Baseline (PP Analysis Set) [KFR]	PP	TPT004
	Descriptive statistics of relative changes from baseline in FEV ₁ and PEF results per parameter and analysis time point. Table sorted by analysis time point. Only post-baseline analysis time points are shown.		
14.3.7.3.1	Primary Objective: Statistical Analysis of Relative Change from Baseline in FEV₁ at 15 Min Post-dose (Safety Set) [KFR]	SAF	ANT001
	Results from the primary objective ANCOVA on relative change from baseline in FEV ₁ at the 15 min post-dose time point as described in section 2.5.3.		
14.3.7.3.2	Statistical Analysis of Relative Change from Baseline in FEV₁ at 15 Min Post-dose (PP Analysis Set) [KFR]	PP	ANT001
	Results from the ANCOVA on relative change from baseline in FEV ₁ at the 15 min post-dose time point as described in section 2.5.3.		
14.3.7.4	Statistical Analysis of Relative Change from Baseline in FEV₁ at Other Time Points (Safety Set) [KFR]	SAF	ANT002
	Results from the ANCOVA on relative change from baseline in FEV ₁ at all other post-dose time points (5 min, 30 min, 1 h, 1 h 30 min and 3 h) as described in section 2.5.3.		
14.3.7.5	Statistical Analysis of Change from Baseline in FEV₁ (Safety Set) [KFR]	SAF	ANT002
	Results from the ANCOVA on absolute change from baseline in FEV ₁ at all post-dose time points (5 min, 15 min, 30 min, 1 h, 1 h 30 min and 3 h) as described in section 2.5.3.		

	Statistical Analysis Plan	
CLI-05993AB6-07		Final 1.0 of 22DEC2022

Number	Title	Analysis Set	TLFs Library Template Number
14.3.7.6	FEV₁: Abnormal Relative Changes from Baseline (Safety Set)	SAF	EGT008

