9. APPENDICES

9.1 SAS CODE

The SAS code in this section is an example and might differ from the actual code used in the statistical analysis.

Lung function ANCOVA models:

```
proc mixed;
  by param atptn;
  class trtan subjid aperiod;
  model (p) chg = trtan subjid aperiod base;
  lsmeans trtan / diff alpha= 0.05;
run;
```

Statistical Analysis Plan

CLI-05993AB6-07

Final 1.0 of 22DEC2022

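### Is the primary analysis left without a decision rule because the ±10% equivalence limits appear only in the sample-size text?

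*Protocol*

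**What the plan says.** The equivalence rule stands in the sizing text. Protocol 12.1 sizes the study for the 15-minute relative change in FEV1, "with equivalence defined as a difference between the two treatments within the 10"% on either side of zero. SAP 1.3 repeats this: 20 evaluable subjects give 95% power for the 95% CI of the mean difference to lie "within the above-mentioned equivalence limits (i.e. [-10%; +10%]) assuming a within-subject standard deviation (SD) of 8"%. The protocol synopsis carries the same rule in its sample-size row, directly above the row that describes the primary ANCOVA.

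The analysis text is separate. Protocol 12.3.6 and SAP 2.5.3 specify an ANCOVA with treatment, subject and period as fixed effects and the period baseline as covariate, from which "the adjusted mean difference between HFA-152a and HFA-134a with their 95% CIs and p-values will be estimated by the model". SAP 2.5.3 introduces it under the label "Primary objective (i.e. evaluation of the potential for bronchoconstriction of each propellant". SAP 2.5.4 adds: "This tables will also include the type III p-values associated to model effects". Table 14.3.7.3.1 is described as "Results from the primary objective ANCOVA on relative change from baseline in FEV"1 at 15 minutes, on the Safety set. The example code in SAP 9.1 has "lsmeans trtan / diff alpha= 0.05". None of these places names the limits.

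Protocol 12.2 uses the Safety population for all safety variables and the per-protocol population for sensitivity.

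**The concern.** The trial was sized to verify equivalence, yet the section that produces the result never says how equivalence is concluded. It also prints p-values with no stated purpose. The type III p-value for a two-level treatment factor tests a difference of zero (F equals t squared), and the same is very likely true of the p-value on the adjusted difference. No test against ±10% is planned. One table would therefore hold an interval that answers the equivalence question and a p-value that answers another.

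If the p-value were taken as the verdict, two errors would be possible. A non-significant result could be read as no added bronchoconstriction although the interval crosses a limit. A significant result could be read as harm although the whole interval lies inside the limits. The first would matter most, because Protocol 1.2 says the study was conceived to answer a regulatory concern about bronchoconstriction that earlier studies could not detect.

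**Working it through.** **1. Is the rule complete without the analysis section?** Each element needed for a verdict can be located:

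| Element | Value | Where fixed |
|---|---|---|
| Variable and time | Relative change from baseline in FEV1, 15 min | Synopsis; Protocol 12.1; SAP 1.3 |
| Contrast | HFA-152a versus HFA-134a | same |
| Limits | −10% to +10% | same |
| Interval | 95% CI | same |
| Model giving the interval | ANCOVA: treatment, subject, period, baseline | Protocol 12.3.6; SAP 2.5.3 |
| Main analysis set | Safety; per-protocol as sensitivity | Protocol 12.2 and 12.3.6; SAP 5.1.1 |

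Only the Safety-set table (14.3.7.3.1) has the primary objective in its title; the per-protocol table (14.3.7.3.2) does not. Neither document gives another margin or confidence level, a superiority hypothesis, or a p-value threshold for success.

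**2. Does the reported interval match the one used for sizing?** Inputs: n = 20, within-subject SD 8%, limits ±10, two-sided 95% CI. The true difference is taken as 0, an assumption.

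- SE = 8 × √(2/20) = 2.530
- Normal approximation: 10/2.530 − 1.960 = 1.993, so power = 2Φ(1.993) − 1 = 95.4%, which reproduces the stated 95%
- 20/(1 − 0.16) = 23.8, so 24 randomised, as stated

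The sizing figure is therefore the power of the interval-inclusion rule at the same 95% level that the primary model reports.

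**3. How often do the p-value and the interval rule differ?** With 18 df, t = 2.101 and the half-width at SD 8% is 2.101 × 2.530 = 5.315. At that half-width, equivalence needs an observed difference below 10 − 5.315 = 4.685 in size, and p < 0.05 needs one above 5.315. The baseline covariate takes one more df (40 observations − 1 intercept − 19 subjects − 1 treatment − 1 period − 1 baseline = 17), giving t = 2.110 and a half-width of 5.337.

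Exact rates, with the observed difference normal and the variance estimate chi-square, integrated over the estimated SD:

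| n, SD, df | True difference | Non-significant, not equivalent | Significant, equivalent | Sum |
|---|---|---|---|---|
| 20, 8%, 18 | 0 | 4.9% | 2.3% | 7.2% |
| 20, 8%, 17 | 0 | 5.2% | 2.4% | 7.6% |
| 20, 8%, 18 | −5 | 14.5% | 7.4% | 21.9% |
| 24, 8%, 22 | 0 | 1.3% | 3.3% | 4.6% |
| 24, 8%, 22 | −5 | 5.9% | 14.7% | 20.6% |

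In the first row the other two cells are 90.1% (non-significant and equivalent) and 2.7% (significant and not equivalent). The equivalence rate is 90.1 + 2.3 = 92.4%, the exact-t power at 20 evaluable; the gap from 95.4% comes from the normal approximation and has no bearing on which statistic decides. An SD of 12%, which is not in the documents, gives 53.8% non-significant and not equivalent at a true difference of 0. There the power for equivalence is only about 41%, so that figure mainly shows an underpowered trial.

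**4. Would restating the rule alter any of this?** No. The model, interval, p-values and analysis sets would stay as they are, so every rate above would be the same. In each disagreeing trial the interval already gives the verdict under Protocol 12.1. The interval also carries the p-value's information, since a 95% CI that excludes zero is the same event as p < 0.05 from the same model. At a true difference equal to a limit, the interval rule declares equivalence in 2.5% of trials, with or without the restatement.

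**The case for a change.** The best argument for acting is that sizing text says what the number of subjects was chosen for; it does not, strictly, say how the result will be judged. A verdict rule should not need assembling from three sections, and p-values without a declared role invite selective reading, above all where absence of a significant difference is not evidence of safety. The SAP was written to be more detailed than the protocol and could have joined the pieces in one sentence.

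The textual part of this stands: no visible analysis section or table names the limits or says that the p-values are descriptive. Blacked-out words in the objective do not explain it, because the analysis paragraphs read complete without a margin. What does not follow is that the verdict is open. Protocol 12.1 belongs to the statistical methods section, uses the word equivalence, and defines it by limits and a confidence level. Reaching a different verdict would mean setting aside the only success definition in either document in favour of a p-value to which no threshold is attached.

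**Conclusion.** The concern is accurate about where the words stand but does not call for a change. The rule was set in advance, it is the only one, and the planned primary analysis on the Safety set delivers the statistic it needs at the right confidence level. An analyst following the plan would conclude equivalence if, and only if, the 95% CI of the adjusted difference lies within ±10%, and would treat the p-values as descriptive.

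The size is nil for the estimate, interval, sample size and error rates. The 7.2% disagreement (4.6% if all 24 are evaluable) assumes a true difference of zero; the larger figures need an assumed difference of −5 points or an assumed SD of 12%, neither of which is in the documents. None of them measures wrong conclusions. Citing the limits beside the primary result when it is reported would help a reader, but that is a matter of presentation and needs neither a protocol amendment nor a change to the analysis.
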